**Figure 8 Study Protocol for SA 1**

[figure not shown]

Table 2 – Aims 1 and 2	
Primary Outcomes	Measurement Tool
Copeptin	ThermoFisher Kryptor Plus
GFR	Iohexol clearance
ERPF	PAH clearance
Renal O 2	BOLD-MRI
Renal perf.	ASL-MRI
Secondary Outcomes	
RVR	MAP/RBF (Table 3)
eGFR	Creatinine, cystatin C
Albumin excretion	Albumin-to-creatinine ratio (ACR)

**Hyperglycemic insulin clamp:** One IV will be placed in each arm to clamp the blood glucose concentrations between 170-190 mg/dL. One IV will be used to administer the boluses of iohexol and PAH in addition to a variable infusion of 20% dextrose and insulin, and the other IV will be used for blood draws. Blood glucoses will be measured every 10 minutes at the bedside, and glycemic control will be achieved using the modified and simplified insulin clamp methodology to remove glycemic effects on GFR and ERPF. The rate of insulin is adjusted based on blood specimens drawn every 10 minutes (example algorithm). Patient blood glucose (BG) levels will be checked at 8am, and adjusted to reach and maintain mild hyperglycemia up until 10am. If participant BG <70mg/dl, we will give 4 oz juice and re-test BG in 15 min. If still <70mg/dl, another 4 oz juice will be given, and BG will be re-tested 15 min later. If still <70 mg/dl,

study MD will be called, and IV D20 will be started at 100ml/hr. For BG between 70-180 mg/dL, a variable D20 infusion will be given on a sliding scale based on participant current BG and weight, as used in previous and current studies (COMIRB #13-0122, #16-1752, #18-0704). Once BG  $> 190$ mg/dl, D20 will be discontinued. If BG is not responding to changes within 2 hours or if increases above 200 mg/dl, a study physician will be contacted. Each time blood is drawn during the clamp, blood will be drawn to a clear line in the syringe to ensure there will be no IV fluid dilution and will be re-infused into the subjects after obtaining the blood sample to minimize blood loss. A blood glucose range of 170-190mg/dL (mild

hyperglycemia) was chosen to limit the acute effects of severe hyperglycemia on GFR and ERPF reproducibility, while allowing us to assess renal function in a glycemic milieu similar to the participants native

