RVR and Gomez equations (Table 3): RVR will be calculated as  $\text{RVR} = \text{MAP}/\text{RBF}$ . To derive additional information about intrarenal hemodynamic function we will use mathematical equations by Gomez et al (55). By using measurements of GFR, RBF, ERPF, renal vascular resistance, hematocrit and serum protein, we can calculate afferent and efferent arteriolar resistance ( $R_A$  and  $R_E$ ), glomerular pressure ( $P_{GLO}$ ) and filtration pressure (Table 3).

Albumin excretion: ACR and AER be determined from 4 hr. urine collection.

Copeptin: Copeptin will be measured by ultrasensitive assays on KRYPTOR Compact Plus analyzers using the commercial sandwich immunoluminometric assays (Thermo Fisher Scientific, Waltham, MA). The copeptin assay has a lower limit of detection of 0.9 pmol/L, and a sensitivity of <2pmol/L. Elevated copeptin will be defined as  $>13 \text{ pmol/L}$ , which is  $>97.5^{\text{th}}$  percentile for healthy adults (68).

Estimated GFR: As an exploratory aim, we will evaluate the agreement between measured GFR (iohexol) with estimated GFR by serum creatinine and cystatin C. Due to the expected normal to elevated GFR for youth with T1D, we will calculate eGFR by Zappitelli equation ( $\text{eGFR} = 25.38 * (1/\text{serum cystatin C})^{0.331} * (1/\text{serum creatinine})^{0.602} * (1.88 * \text{height})$ ) (69-71).

[figure not shown]

Table 3 Measures	Definition:
Filtration fraction (FF)	$\text{FF} = \text{GFR} / \text{RPF}$ (renal plasma flow)
Renal blood flow (RBF)	$\text{RBF} = \text{RPF} (1-\text{Hct})$
Renal vascular resistance (RVR)	$\text{RVR} = \text{MAP}/\text{RBF}$
Filtration pressure $\Delta P_F$	$\Delta P_F = \text{GFR}/K_{FG}$ , $K_{FG}$ : filtration coefficient
Mean plasma protein ( $C_M$ )	$C_M = \text{total protein} / \text{FF} \times \text{natural log} (1/1-\text{FF})$
Glomerular oncotic pressure ( $\pi_G$ )	$\pi_G = 5 \times (C_M - 2)$
Glomerular pressure ( $P_{GLO}$ )	$P_{GLO} = \Delta P_F + P_{BOW} + \pi_G$ , $P_{BOW}$ is 10 mmHg
Afferent arteriolar resistance ( $R_A$ )	$R_A = [(MAP - P_{GLO})/\text{RBF}] \times 1328$
Efferent arteriolar resistance ( $R_E$ )	$R_E = [(GFR/K_{FG} \times (RBF-GFR))] \times 1328$

Blood pressure: After participants have been laying supine for a minimum of 5 minutes, blood pressure measurements will be obtained using an automatic blood pressure machine and 3 measurements will be averaged. MAP will be calculated from the blood pressure readings.

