### ***Aim 1 - Expected outcomes and limitations:***

We expect copeptin to be greater in T1D youth with hyperfiltration vs. those without hyperfiltration. In youth with short-standing T1D and hyperfiltration, we anticipate that copeptin concentrations will positively correlate with GFR, ERPF, RVR, glomerular pressure and albumin excretion. We theorize that elevated AVP results in afferent arteriolar vasodilation with resultant increased ERPF and glomerular pressure which leads to hyperfiltration (Fig 10). Furthermore, a mild hyperglycemic clamp allows us to quantify intrarenal hemodynamic function in a glycemic milieu similar to their native pathophysiology. In contrast, a hyperinsulinemic-euglycemic clamp would render the participants completely normoglycemic, which does not reflect their usual glycemic environment, and expose them to high concentrations of insulin which may interfere with the assessment of their intrarenal hemodynamic function. Most studies focus on the classical definition of hyperfiltration which disregards ERPF and  $P_{GLO}$ . Our proposed project addresses these concerns and others in regard to scientific rigor, by also examining hyperfiltration defined as  $FF (GFR/ERPF) > 17.7\%$  and calculating  $P_{GLO}$  by Gomez' equations (67, 121). The sustained hypermetabolism of hyperfiltration is thought to initiate the development of nephropathy as the energy profile of T1D cannot accommodate the increased energy demand which leads to progressive nephron loss (122-127). We hypothesize that the elevated AVP activity in T1D may play a role in initiating hyperfiltration through vasodilation of the afferent arterioles with increased ERPF and glomerular hypertension (Fig 10).

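### Table 3 prints the mean plasma protein formula so that it evaluates negative, and the eGFR equation has no units and should be checked against its cited sources before coding

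*Combined protocol and SAP*

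**What the plan says.** Section IV, Table 3, lists the formulas for the derived intrarenal measures. The row labelled "Mean plasma protein" reads "C_M = \text{total protein} / \text{FF} \times \text{natural log} (1/1-\text{FF"). The next rows set glomerular oncotic pressure to 5 × (C_M - 2), then "P_{GLO} = \Delta P_F + P_{BOW} + \pi_G" with P_BOW fixed at 10 mmHg, then R_A as (MAP - P_GLO)/RBF × 1328. Filtration fraction is GFR over renal plasma flow. Section E (Aim 1, expected outcomes) also uses it as a cut-off, "FF (GFR/ERPF) > 17.7" percent.

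The same table gives RBF as RPF multiplied by (1-Hct), and R_E as GFR/K_FG multiplied by (RBF-GFR), then by 1328.

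Under Estimated GFR in section IV the plan says "we will calculate eGFR by Zappitelli equation" and cites references 69-71. The equation starts with 25.38, raises inverse cystatin C to the power 0.331, and ends with "1/\text{serum creatinine})^{0.602} * (1.88 * \text{height"). It gives no unit for cystatin C, creatinine or height. Its stated use is "As an exploratory aim, we will evaluate the agreement between measured GFR (iohexol) with estimated GFR by serum creatinine and cystatin C". Table 2 lists eGFR ("Creatinine, cystatin C") among the secondary outcomes.

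**The concern.** A methods formula should give the intended result when someone codes it as written. The C_M row does not. By normal operator order, 1/1-FF is 1-FF, which is below 1, so its logarithm is negative and plasma protein comes out negative.

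C_M is the first step of a chain that ends in P_GLO and R_A. H1.2 covers intrarenal hemodynamics, section G (Aim 1) regresses the Gomez-derived parameters on copeptin, and section E presents P_GLO as part of the study's rigor.

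The eGFR equation raises a different doubt. An equation fitted as a product has no reason to carry two separate multipliers, because 25.38 × 1.88 = 47.7 would do the same work. The structure is therefore suspect, and without units the equation cannot be run without a guess. At stake are a secondary outcome and the exploratory agreement analysis, where a coding error would be reported as bias of estimated GFR.

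**Working it through.** The documents give no worked value of C_M, P_GLO or eGFR, so there is no stated figure to reproduce. I evaluated the formulas directly.

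**Assumed inputs.** Total protein 7 g/dL (range 6-8), FF 0.20 (range 0.15-0.30), K_FG 0.08-0.12 ml/s/mmHg, hematocrit 0.40 (range 0.36-0.45). GFR of 135 ml/min is the plan's hyperfiltration threshold, equal to 135/60 = 2.25 ml/s.

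**1. C_M.**
- As printed: 7/0.20 × ln(1/1 - 0.20) = 35 × ln(0.80) = 35 × (-0.2231) = -7.81.
- With brackets: 35 × ln(1/0.80) = +7.81.
- At the plan's FF cut-off of 0.177: -7.70 against +7.70.

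Only the sign changes. Placing the log in the denominator, total protein/(FF × ln(1/(1-FF))), gives 56 to 328 over the assumed ranges, so it is not a workable reading.

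**2. Oncotic pressure, 5 × (C_M - 2).** As printed 5 × (-9.81) = -49.1 mmHg; with brackets 5 × 5.81 = +29.1 mmHg.

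**3. P_GLO.** At K_FG 0.10, filtration pressure is 2.25/0.10 = 22.5 mmHg.
- As printed: 22.5 + 10 - 49.1 = -16.6 mmHg.
- With brackets: 22.5 + 10 + 29.1 = 61.6 mmHg.
- Over K_FG 0.08-0.12: -11 to -20 against 67 to 58 mmHg.

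The gap between the two readings is 10 × C_M, whatever K_FG is. With C_M from 6.50 (FF 0.15, protein 6) to 9.51 (FF 0.30, protein 8), it runs from 65 to 95 mmHg. It differs between participants, so literal coding would distort regression slopes as well as the mean. MAP - P_GLO, the numerator of R_A, is too large by the same amount.

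**4. Other Table 3 rows.**
- RBF: plasma is a fraction (1-Hct) of blood, so blood flow must exceed plasma flow. The printed product makes it smaller. At RPF 700 and Hct 0.40 it gives 420, against 700/0.60 = 1,167, a ratio of 0.36. RVR = MAP/RBF, a secondary outcome, is then 1/0.36 = 2.8 times too high (2.4 to 3.3 over Hct 0.36-0.45).
- R_E: GFR/K_FG is a pressure, and the R_A row is pressure divided by flow, times 1328. As bracketed, R_E is pressure multiplied by flow, so the two resistances do not share a dimension.

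**5. eGFR units.** Assumed cystatin C 0.8, creatinine 0.6, height 165 cm.
- Common part: 25.38 × (1/0.8)^0.331 × (1/0.6)^0.602 = 37.16.
- Height in metres: 37.16 × 1.88 × 1.65 = 115.
- Height in centimetres: 37.16 × 1.88 × 165 = about 11,500.

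For the printed product, only metres gives a usable value.

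**6. eGFR form (conditional).** If the source has 1.88^height in metres, the ratio printed/source is (1.88 × h)/(1.88^h):

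| Height (m) | Printed form too high by |
|---|---|
| 1.35 | 8.2% |
| 1.50 | 9.4% |
| 1.58 (peak) | 9.6% |
| 1.70 | 9.3% |
| 1.80 | 8.6% |
| 1.90 | 7.6% |

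In the example, 115 would be 105. If the source instead had height^1.88, the gap would be (1.88 × 1.65)/(1.65^1.88) - 1 = 21% at 1.65 m, about 40% at 1.4 m and 7% at 1.9 m. The documents do not choose among these forms.

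**The case against.** The C_M row is a notation slip. Bracketing 1-FF is the only reading that gives usable values, and a programmer who coded the line literally would see negative plasma protein in every participant. Section III reports that the team has already derived P_GLO, R_A and R_E with Gomez's equations and obtained interpretable results, and section IV cites a source for them. A stacked fraction in the typeset table would also remove the ambiguity. All of this lowers the chance of harm. The printed line still gives a wrong result when followed.

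On eGFR, two multiplying constants are redundant but not mathematically wrong, and one could be a scaling or unit constant. The product in metres gives a plausible 115. The structural argument justifies a check and does not prove an error.

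Three stronger readings are tempting and unsupported:
- A reader might infer that eGFR is overstated by 8-10%. The power form appears nowhere in the documents, so that figure is conditional on an unverified source.
- A reader might infer that participants would move across 135 ml/min/1.73m². Section IV defines hyperfiltration on iohexol GFR, and the alternative FF definition also uses measured clearances. The screening labs include no cystatin C, so this equation is not shown to drive eligibility either.
- A reader might infer that P_GLO and R_A will be wrong in the results. That requires literal coding that nobody notices.

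**Conclusion.** The C_M formula is wrong as printed and should be corrected. Followed literally, it reverses the sign of plasma protein for every FF between 0 and 1, which needs no assumption. It lowers P_GLO by 10 × C_M, about 78 mmHg at the assumed protein of 7 g/dL and FF of 0.20. The RBF and R_E rows fail on internal grounds, and the RBF row touches a secondary outcome that the C_M correction would leave untouched. The same caution about typesetting applies to both.

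The eGFR equation is unverified and cannot be run as printed without guessing units. The redundant constant is a reason to check it. The possible overstatement of about 8-10% holds only if the source has 1.88 to the power of height in metres, and it would then appear as bias in the agreement analysis. The hyperfiltration groups, and the measured GFR and ERPF outcomes, do not depend on any of these formulas.

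**What to change.** 1. Print the C_M log term as ln(1/(1-FF)), with FF as a proportion.
2. In the same pass, proofread all of Table 3 against the cited source for Gomez's equations, in particular the RBF row and the bracketing of R_E, and state the units of GFR, RBF and K_FG.
3. Check the eGFR equation against references 69-71, state the units of cystatin C, creatinine and height, and change the height term only if the source differs.
4. Before analysis, run one worked example through the code and confirm that C_M, oncotic pressure and P_GLO are positive and that RBF exceeds RPF.

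The cost is a short editorial correction before coding. Sample size, procedures and data collection are unaffected.

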**Table 1: Eligibility Criteria**

Inclusion criteria	Exclusion criteria
Antibody+ T1D with $<10$ yr duration	Severe illness, recent DKA
Age 12-21 years	ACEi, ARB, diuretics, SGLT 2/1 blockers, atypical antipsychotics, steroids
BMI $\geq 5\text{ percentile}$	Macroalbuminuria ( $>300\text{mg/g}$ ) or eGFR $<60\text{ml/min}/1.73\text{m}^2$
Weight $<300$ lbs.	Pregnancy, nursing
HbA1c $<12\%$	Anemia or allergy to shellfish or iodine
BP $< 140/90\text{ mm Hg}$	

intrarenal hemodynamic function. They will also be provided with a 3-day diet instructions (45% carbohydrates, 30% fat, 25% protein and a goal of 3.45 g salt/day), with females studied in the follicular phase of the menstrual cycle where possible to limit impacts of nutrient and menstrual hormone variations on IR and renal function, as previously described (61). Participants will ask to administer their long

acting insulin (e.g. Lantus or Levemir) like they normally would. Patients on insulin pumps can remain on their basal rate throughout the study. If on a hybrid-closed loop (artificial pancreas), participants will be asked to open their loop for the duration of the study. The morning of the study, participants will be asked to check their blood sugar prior to arriving at the CTRC. If their blood sugar is  $\geq 250$  mg/dL, they will be asked to administer a bolus of short acting insulin using their home correction factor with a blood sugar target of 200 mg/dL.

Participants will arrive the evening before, or present fasting in the morning and have 2 IVs placed and have their blood glucose concentrations clamped in the mild hyperglycemic range (details below) (Fig 8). Baseline blood will be drawn for serum copeptin, lipids, insulin, cystatin c, creatinine, sodium, hematocrit and total protein, and iohexol and PAH boluses given via IV (see below for details). GFR and ERPF will be measured by iohexol and PAH clearance in plasma. A 4 hr urine sample will be collected to calculate ACR and AER.

**Specific methods:** Outcomes are summarized in **Table 2**. Detailed methods are listed below:

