Metabolomics: We will measure serum metabolomics by Q Exactive UHPLC-MS Analysis at the Metabolomics Core Facility Services at University of Colorado ([name] [name], PhD).

Urine and serum osmolality: We will directly measure urine and serum osmolality using freezing point method with Micro-Osmometer Model 3300 (Advanced Instruments, Massachusetts, USA) at [name]'s Lab.

Fractional excretion of sodium (FeNa): We will measure serum and urine sodium and creatinine to calculate fractional excretion of sodium.

DXA: Participants will also undergo DXA by standard methods on a Hologic device (Waltham, MA) to determine lean and fat mass (72).

Renal oxygenation and renal perfusion by MRI: The primary outcomes of Aim 2 are renal oxygenation and perfusion (**Table 2**). We will perform BOLD MRI (73) to quantify renal oxygenation, whereas renal perfusion will be measured by ASL (74)(**Table 2**). These studies will be performed at the UCD Research Imaging Center (3T Siemens Skyra scanner) which already has an active renal BOLD-MRI protocol as part of the multi-center COMBINE (CKD Optimal Management with Binders and Nicotinamide) study (**Table 4**) (75), for which our collaborator [name] directs the CORE for trouble-shooting and analyzing the renal MRIs. [name] is an international leader in advanced MR research and will provide the techniques for BOLD and ASL MRI acquisition and analyses.

[figure not shown]
Table 4. MRI protocol_3T Skyra				BOLD	ASL
Series	Localizer				
Plane	2 Plane	Coronal	Axial	Coronal	Coronal
Pulse sequence	gre	gre	gre	gre	Custom
TR/ms	7	7	7	61	3000
TE/ms	2.66	2.66	2.66	4.92, 9.84, 14.76, 19.68, 24.6, 29.52, 34.44, 39.36	1.92
Read out mode	n/a	n/a	n/a	Bipolar	n/a
In line mapping	n/a	n/a	n/a	T2* (VB 17)/R2* (VD 13) Map	n/a
BW Hz/pixel	290	290	290	260	501
FOV mm	400	400	400	400	400
Slices	3 ax, 3 cor	5	5	5	1
Concatenation	6	5	5	5	1
Slice Thickness / mm	8	8	8	5	8
Skip	50%	50%	50%	0	n/a
Fat suppressed	No	No	No	Fat Sat	n/a
Parallel Imaging acceleration factor	None	None	None	None	None
Diffusion mode	n/a	n/a	n/a	n/a	n/a
B value s/mm 	n/a	n/a	n/a	n/a	n/a
Diff. gradients	n/a	n/a	n/a	n/a	n/a
NEX	2	2	2	1	50
Acq-matrix	154x256	154x256	154x256	192x256	128x128
Flip angle/degrees	20	20	20	30	60
Typ. Scan time m:s	0:14	0:07	0:07	0:30-1:00 (5 slices)	0:05

Options/commnts	Site preference	Instruct subjects to not to take deep breaths	Changing FOV and/or matrix size not preferred	Instruct subjects to not to take deep breaths.

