-----------------	-----------------	---	---	---

**Abbreviations:** BOLD: Blood oxygen level dependent, SSFP: steady state free precession, VLA: vertical long axis view, LVOT: left-ventricular outflow tract view, GRE: gradient recalled echo.

**Recruitment:** Ultimately 50 youth with T1D (50% male) will be enrolled (see power analysis). Recruitment will begin year 1 and will consist of adolescent patients with type 1 diabetes from the Barbara Davis Center for Childhood Diabetes (BDC), where principal investigator [name] and co-investigator Drs. [name] and [name] are medical providers and have weekly clinics. The investigator team has excelled when recruiting adolescent T1D patients. There are almost 4000 pediatric patients actively followed at BDC, and we do not foresee any difficulties with recruitment.

**Detailed Study Visit Descriptions:** The study timeline for is illustrated in **Fig 10**, and details from each study visit is summarized below. Visit 1 is the screening visit and visit 2 and 3 will occur consecutively.

**Visit 1 (Screening visit):** Prescreening will be done by phone or in conjunction with a clinical diabetes visit. The full screening visit will include the consent process, history, allergies confirmed, physical exam, and screening labs (HbA1c, hemoglobin and hematocrit [H&H], serum creatinine, urine microalbumin to creatinine ratio). All females will also have a pregnancy test and detailed menstrual history. The screening visit will take approximately 2 hours.

**Visit 2, part 1:** Participants will present the evening before the study visit, or present fasting to the Pediatric CTRC in the morning, and have IV(s) placed. Fasting blood will be drawn for serum copeptin, lipids, insulin, cystatin c, creatinine, sodium, hematocrit and total protein prior to the clamp. Participants will be escorted to the Brain Imaging Center or CHC Radiology for a BOLD and ASL MRI per local protocol. BOLD MRI measurements will be performed at baseline and following administration of a small dose of furosemide (20 mg IV) via the PIV. A study physician or nurse will be responsible for the furosemide administration. Total duration of part 1 will be approximately 1.5 hours.

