**Visit 2, part 2:** Participants return to pediatric CTRC and will have their blood glucose concentrations clamped in the hyperglycemic range. Participants will also undergo iohexol and PAH clearance studies, in addition to 4-hour urine collection for album excretion rate (AER) and albumin to creatinine ratio (ACR). Upon completion of visit 2, participants will be provided with a study meal (lunch). After lunch, participants will undergo DXA scan for quantification of body composition. This concludes the study. Total duration 6 hours.

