#### **Aim 2 - Expected outcomes and limitations:**

We expect increased renal perfusion and renal O2 consumption in T1D youth with hyperfiltration. We also anticipate a strong correlation between copeptin, renal perfusion and renal O2. Based on our preliminary work, we expect the 2 renal sequences (BOLD and ALS) to be completed within 60 min. [name] NIH R56, JDRF and ADA studies had adolescents with T1D, T2D and without diabetes undergo similar MRI procedures lasting 120 min, indicating that recruiting and tolerability in youth for such procedures are feasible. Our research MRI is equipped with in-MRI movie-viewing with noise-cancelling headphones and thus is very tolerable to youth. The participant will be monitored by heart rate, blood pressure, and oxygen saturation measurements, and will be able to communicate with the MRI technician and investigator immediately outside of the scanner. As BOLD is potentially influenced by O2 delivery (ERPF) and O2 consumption (tubular Na transport accounts a majority of renal O2 consumption (128)) we will control for ERPF and fractional excretion of sodium (FeNa). We will perform the MRI fasting in the morning to remove the effects of acute glycemic variations on RPF and the impact of changes in hydration status of renal oxygenation. Participants on medications that might alter O2 delivery and/or consumption, e.g. angiotensin-converting enzyme inhibitors (ACE-I), angiotensin receptor blockers (ARBs) and diuretics will be excluded.

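### The visible text describes no urine taken before furosemide at Visit 2, so the FeNa adjustment in Aim 2 may not describe the kidney at the baseline BOLD scan

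*Combined protocol and SAP*

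**What the plan says.** **Order of events.** Under Detailed Study Visit Descriptions, Visit 2, part 1 lists a fasting blood draw that includes serum sodium and creatinine, followed by the MRI. Furosemide falls between the two BOLD acquisitions: "BOLD MRI measurements will be performed at baseline and following administration of a small dose of furosemide (20 mg IV) via the PIV". No urine is listed in part 1. In part 2 participants return to the research unit for the clamp, and "Participants will also undergo iohexol and PAH clearance studies, in addition to 4-hour urine collection for album excretion rate (AER") and ACR. The MRI paragraph of section D.7 confirms that the clamp comes after the furosemide.

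**Purpose of the 4-hour urine.** The study design text says "A 4 hr urine sample will be collected to calculate ACR and AER". The albumin excretion paragraph of Specific methods agrees: "ACR and AER be determined from 4 hr. urine collection". Neither mentions FeNa.

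**FeNa.** Specific methods says "We will measure serum and urine sodium and creatinine to calculate fractional excretion of sodium". It gives no specimen or time. The urine osmolality paragraph beside it gives none either.

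**Use of FeNa.** Section E, Aim 2, explains that BOLD reflects both oxygen delivery and oxygen consumption, the latter driven mostly by tubular sodium transport. For that reason "we will control for ERPF and fractional excretion of sodium (FeNa"). The same paragraph sets the scan conditions: "We will perform the MRI fasting in the morning to remove the effects of acute glycemic variations on RPF". In section G, Aim 2, FeNa enters as the addition that turns Model 3 into Model 4, within a set of models offered as examples.

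**The concern.** FeNa is in the model to represent tubular sodium handling, and through it oxygen consumption, when the BOLD signal was acquired. A covariate can do that only if it is measured in the same physiological state as the outcome. The baseline scan is fasting and before furosemide. The one urine described for chemistry is collected after an intravenous diuretic and under a glucose clamp.

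The plan itself treats diuretic exposure as relevant here: section E, Aim 2, excludes participants on diuretics because such drugs may change renal oxygen delivery or consumption.

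If the 4-hour urine supplies FeNa, Model 4 would appear to adjust for oxygen consumption at baseline while adjusting for a later, altered state. The outcomes concerned, renal oxygenation and perfusion, are primary for Aim 2. Naming a specimen afterwards cannot repair this, because a pre-dose urine not collected that morning cannot be recovered.

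**Working it through.** No sample size, power or alpha figure is in dispute, so the check is to trace each specimen and its timing.

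**Step 1: specimens in the order described.**

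| Point | State | Urine described |
|---|---|---|
| Visit 1, screening | before any study drug | screening ACR; no sodium listed |
| Visit 2 part 1, fasting blood (serum sodium, creatinine) | fasting | none |
| Visit 2 part 1, baseline BOLD | fasting, pre-dose | none |
| Visit 2 part 1, furosemide, repeat BOLD | post-dose | none |
| Visit 2 part 2, clamp at 170-190 mg/dL with iohexol and PAH | post-dose, clamped | 4-hour collection, for ACR and AER |
| DXA | after the study lunch | pregnancy test beforehand (females); not assigned to FeNa |

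Pre-furosemide urines described at Visit 2 for chemistry: 0. Section D.7 and Table 6 mention urine samples without type or time, so they do not change the count.

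**Step 2: what FeNa needs.** FeNa = 100 x (urine sodium x serum creatinine) / (serum sodium x urine creatinine). The two serum terms are in the fasting draw. The two urine terms have no described pre-dose source. The plan does not say which serum would be used; if it were the fasting serum with the 4-hour urine, one ratio would mix pre-dose and post-dose specimens.

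**Step 3: which analyses are touched, if FeNa comes from the 4-hour urine.**

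- Models 1 to 3 contain no FeNa and are unaffected.
- Model 4 for baseline R2*, or for the baseline medulla-minus-cortex difference defined in section G: FeNa and outcome come from different states.
- Model 4 for ASL perfusion: the same if ASL is acquired before the dose. Its timing relative to the dose is not stated.
- Model 4 for the pre-minus-post R2* difference: the outcome spans the dose, so a post-dose FeNa is not clearly wrong. The plan does not say which FeNa applies.

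**Step 4: size.** It would depend on how closely the 4-hour FeNa tracks the fasting FeNa, and on how FeNa relates to copeptin or hyperfiltration and to the MRI measures. The documents give none of these. The interval from dose to urine is not stated and cannot be firmly bounded: the itemised visit times sum to 2 + 1.5 + 6 = 9.5 h, against about 11 h in section D.2, leaving 11 - 9.5 = 1.5 h unplaced.

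**Step 5: the companion control.** Section E, Aim 2, names ERPF alongside FeNa. ERPF comes from the PAH clearance in part 2, so it too is measured after furosemide and under the clamp, and is not matched to the baseline scan.

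**The case against.** The strongest reply is that the plan ties FeNa to no urine at all. The 4-hour collection is assigned only to ACR and AER, so its use for FeNa is an inference. That stands, and the point is therefore conditional. Figure 8 and the study timeline are not visible and could mark a baseline urine; the visit text calls the timeline Fig 10, but the visible caption with that number is for a mechanism diagram. That stands too.

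The possible harm is also narrow. It needs FeNa from the 4-hour urine, a pre-dose outcome, and the last of four example models. Section G says the pre-minus-post BOLD value will be reported, where the objection to a post-dose FeNa is weak. Baseline R2* measures are defined there as well, however, so the issue does not disappear.

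Finally, ERPF has the same mismatch, so a spot urine does not align every control with the scan. This is correct and should be acknowledged. It does not argue against matching FeNa, which one urine can do.

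A reader might infer more than the documents support:

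- **That most of the FeNa confounding would remain in Model 4.** Any such share depends on correlations the documents do not give.
- **That the mismatch differs between the hyperfiltration groups.** One cited paper's title links hyperfiltration to glucose-dependent changes in FeNa, but a title gives neither size nor direction.
- **That ACR and AER are biased because they follow furosemide.** The visit order is already plain, the same dose is specified for all participants, and no bias in their associations has been shown.

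**Conclusion.** The point holds in conditional form. Followed as written, the visible text leaves only a post-diuretic, clamped urine from which FeNa could be calculated at Visit 2. A FeNa from that urine would not serve the stated purpose for baseline BOLD, nor for ASL if acquired before the dose. This goes beyond missing detail, because naming the specimen does not help if no pre-dose urine exists.

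The effect on any estimate cannot be quantified from the documents. The conclusion rests on two assumptions: that no unseen figure marks a pre-MRI urine, and that FeNa would come from the only Visit 2 collection described for chemistry. It concerns one covariate in one example model and does not invalidate Aim 2. It is a cheap improvement worth making before visits take place. Nothing here questions the furosemide dose or its use.

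**What to change.** 1. Collect one spot urine on the study morning with the fasting blood draw, before the MRI and furosemide. The protocol allows two arrival routes ("Participants will present the evening before the study visit, or present fasting to the Pediatric CTRC in the morning"); for those admitted the evening before, use the morning sample rather than one on arrival.
2. State that the fasting serum is drawn before the MRI. Calculate FeNa from this urine and the fasting serum sodium and creatinine, and measure urine osmolality in the same urine. Name the specimen and time in the FeNa and osmolality paragraphs and in Visit 2, part 1.
3. In section G, use this FeNa in Model 4 for baseline BOLD, and for ASL if it is pre-dose. State the ASL timing. Say in advance which FeNa applies to the pre-minus-post outcome.
4. Acknowledge that ERPF, as a control, is measured after furosemide under the clamp and is not matched to the baseline scan.

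If Figure 8 or the study timeline already marks a pre-MRI urine, only the wording needs to change.

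**Cost.** 50 spot urines and 50 x 3 = 150 routine assays (urine sodium, creatinine, osmolality), plus protocol wording. Serum sodium and creatinine are already in the fasting draw. The downside is that a spot FeNa carries its own sampling noise and does not match the clearance period.
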